2.2 Clinical Hypothesis

The clinical hypothesis of the study is that QM1114-DP is safe and effective for the long-term treatment of moderate to severe GL and LCL, and has an acceptable safety profile.

3. OVERALL CLINICAL STUDY DESCRIPTION

This is a phase 3, multicenter, open-label study to evaluate the safety of QM1114-DP for the long-term treatment of moderate to severe GL and LCL.

Eligible subjects will receive up to 4 treatments of QM1114-DP in the GL and/or LCL and will be monitored for safety and efficacy over a period of up to 52 weeks.

The first treatment will be administered at Day 0 (Baseline). Re-treatments can be administered at any of the follow-up visits from Week 12 to Week 40, provided that the subject is eligible for retreatment and there has been at least 12 weeks since the last treatment. Follow-up visits for treated subjects are conducted at Day 7 and Day 14 after each treatment. Follow-up visits, i.e. not treatment dependent, are scheduled at Week 4, 8, 12, 16, 20, 24, 28, 32, 36, 40, 44, 48 and 52.

To ensure a sufficient amount of long-term safety data is included in the database per ICH E1 guidelines, approximately 900 subjects will be enrolled; all subjects will be followed for at least 24 weeks and at least 300 subjects will be followed up to 52 weeks. The study may be stopped when at least 300 subjects have completed the Week 52 study visit.

All subjects that meet the eligibility criteria and are enrolled in the study will be treated on Day 0. Additional treatment can be administered at any of the follow-up visits from Week 12 to Week 40, provided that the following criteria are met:

- It has been at least 12 weeks since the previous treatment.
- Moderate (grade 2) or severe (grade 3) GL and/or LCL at maximum contraction (i.e., frown and smile, respectively) as assessed by the Investigator CCI (ILA CCI). In order to treat LCL, both sides should meet severity criteria and be treated at the same visit.
- There are no ongoing adverse events assessed as related to the treatment, which could exclude the subject from re-treatment.
- Subject agrees to receive re-treatment.
- If the subject is a female of child bearing potential, must be willing to take a pregnancy test
 and the result must be negative in order to receive re-treatment.
- There is no other medical or surgical condition that would put the subject at undue risk in case he/she receives an additional treatment cycle, according to Investigator's judgment.

After each treatment, subjects will return for study visits at Day 7 and Day 14. Follow up visits, i.e. not treatment dependent, are scheduled at Week 4, 8, 12, 16, 20, 24, 28, 32, 36, 40, 44, 48, and 52.

Efficacy assessments will include (Section 7.1):

 4-point Photographic Scale of GL Severity at rest and maximum frown (Investigator assessment [GL-ILA])

CCI

 4-point Photographic Scale of LCL Severity at relaxed position and maximum smile (Investigator assessment [LCL-ILA])

CCI	
CCI	
CCI	

Safety assessments will include (Section 7.2):

- Adverse Events (AEs)
- · Focused physical examination (FPE)
- · Vital signs
- Laboratory safety tests (chemistry and hematology)
- Production of neutralizing antibodies against QM1114-DP

	43QM1903 Clinical Study Protocol - QM1114 - LTS for LCL/GL	Doc id
♣ GALDERMA	45QM11505 Chilical Study 11000c01- QM11114- L15 for LCL/GL	MA-40372

Selection criteria for the study population are described in Section 5. Detailed information about study tasks by treatment visit is outlined in Section 8 and in Table 1. Information regarding clinical supplies and treatment procedure are provided in Section 6.

4. CLINICAL STUDY DURATION AND TERMINATION

The planned duration of recruitment (from first subject first visit [FSFV] to last subject first visit [LSFV]) is approximately 3 months.

The planned clinical study duration from FSFV to last subject last visit (LSLV) is approximately 16 months.

To ensure a sufficient amount of long-term safety data is included in the database per ICH E1 guidelines, approximately 900 subjects will be enrolled; all subjects will be followed for at least 24 weeks and at least 300 subjects will be followed up to 52 weeks. The study may be stopped when at least 300 subjects have completed the Week 52 study visit.

The Sponsor may decide to prematurely terminate or suspend the participation of a particular clinical study center (for example, lack of subject enrollment or non-compliance with clinical study protocol, regulation, or GCP) or prematurely suspend the clinical study (for example, for safety, study product quality, regulatory, efficacy, or logistical reasons) at any time with appropriate notification.

	Title	Doc id
- GALDERMA	43QM1903 Clinical Study Protocol - QM1114 - LTS for LCL/GL	MA-40372

5. SELECTION AND DISPOSITION OF CLINICAL STUDY POPULATION

5.1 Number of Subjects

As a screen failure rate of approximately 10 percent is anticipated, approximately 990 subjects will be screened in order to get 900 subjects enrolled.

It is expected that each center will recruit a similar number of subjects.

5.2 Clinical Study Population Characteristics

In order to be eligible for the clinical study, subjects must fulfill all of the following criteria. These criteria are applicable at both screening and baseline unless otherwise specified.

5.2.1 Inclusion Criteria

- 1. Male or female 18 years of age or older.
- 2. Moderate to severe GL (grade 2 or 3 on the 4-point Photographic Scale ranging from 0 [none] to 3 [severe]) at maximum frown as assessed by the Investigator (GL-ILA).
- 3. CCI
- Moderate to severe bilaterally symmetrical LCL (grade 2 or 3 on the 4-point Photographic Scale ranging from 0 [none] to 3 [severe]) at maximum smile as assessed by the Investigator live assessment (LCL-ILA).
- 5. CCI
- Female of non-childbearing potential (i.e., post-menopausal [absence of menstrual bleeding for 1 year prior to screening, without any other medical reason], or has undergone hysterectomy or bilateral oophorectomy).

OR

Female of childbearing potential with a negative urine pregnancy test at screening and baseline, and agrees to use a highly effective and approved contraceptive method for the duration of the study. A highly effective method of contraception is defined as:

Bilateral tubal ligation;

- Combined (estrogen and progesterone containing) oral, intravaginal or transdermal contraceptives that inhibit ovulation as the primary mode of action, on a stable dose for at least 28 days prior to screening visit;
- Intra uterine device (IUD) inserted at least 28 days prior to screening visit;
- Intrauterine hormone-releasing system;
- Partner vasectomized for at least three months prior to screening visit;
- Progestogen-only oral, injectable or implantable contraceptives that inhibit ovulation as the primary mode of action, on a stable dose for at least 28 days prior to screening visit; or
- Strict abstinence (i.e., refraining from heterosexual intercourse for the entire duration of the subject's participation in the study).
- 7. Time and ability to complete the study and comply with instructions.
- 8. Understands the study requirements and signed the informed consent form (ICF).

5.2.2 Exclusion Criteria

- 1. Previous use of any Botulinum toxin in facial areas within 9 months prior to study treatment.
- 2. Anticipated need for treatment with botulinum toxin of any serotype for any reason during the study (other than the investigational product).
- Female who is pregnant, breast feeding, or intends to conceive a child during the study.
- Known allergy or hypersensitivity to any component of the investigational product (QM1114-DP) or any botulinum toxin serotype.
- 5. Inability to substantially reduce the appearance of facial rhytides in the treatment area by physically spreading them apart, as determined by the Investigator.
- Clinically significant abnormal focused physical exam finding(s) at screening or baseline visits, in the investigator's opinion.
- 7. Excessive skin laxity in the treatment area or periorbital area.
- 8. Previous use of any hyaluronic acid soft tissue augmentation therapy in the glabella or lateral canthus areas within 6 months before baseline.
- Previous soft tissue augmentation with any permanent (non-biodegradable such as silicone, polyacrylamide, etc) or semi-permanent (i.e., calcium hydroxylapatite, poly-L-Lactic acid or polymethyl-methacrylate) product; lifting threads, or autologous fat in the treatment area.
- 10. History, presence, or predisposition of eyelid or eyebrow ptosis (heavy eyebrows), amblyopia (i.e., lazy eye), or previous surgery around the eye that may lead to the above events, as determined by the Investigator.

- Marked facial asymmetry, excessive dermatochalasis (i.e., excess of skin in eyelids), or marked periocular or eyebrow asymmetry.
- 12. Presence of scar(s), piercing(s), or tattoo(s) (including micro blading of eyebrow or eyeliner) in the treatment area or around the treatment area that, in the Investigator's opinion, may interfere with study evaluations.
- 13. Presence of inflammation, active infection or skin disorder, such as eczema, rosacea, facial psoriasis, herpes zoster etc., near or in the treatment area.
- 14. Presence of cancerous or pre-cancerous lesions in the treatment area.
- 15. History of other facial treatment, surgery or other aesthetic procedures (e.g. ablative skin resurfacing, laser treatment, micro needling, chemical peel) in the previous 12 months that, in the Investigator's opinion, could interfere with study injections and/or assessments or expose the subject to undue risk by study participation.
- 16. Planned facial surgery, eye surgery (including LASIK procedure) or aesthetic procedures (e.g. ablative skin resurfacing, laser treatment, micro needling, chemical peel, botulinum toxin treatment, or dermal fillers) in the face during the study period.
- 17. History or presence of facial nerve palsy, or any medical condition that may put the subject at increased risk with exposure to botulinum toxin including diagnosed myasthenia gravis, Lambert-Eaton syndrome, amyotrophic lateral sclerosis, or any other condition that might interfere with neuromuscular function.
- 18. Use of medications that affect neuromuscular transmission such as curare-like depolarizing agents, lincosamides, polymyxins, anticholinesterases, and aminoglycoside antibiotics.
- 19. Subject with bleeding disorder or subject currently using anticoagulants.
- 20. Subject has any prior or current psychiatric illness (e.g. Psychosis, depression, anxiety), alcohol or drug abuse, or is taking antidepressant, anxiolytic, or antipsychotic medication that, in the Investigator's opinion, could affect the subject's safety and/or participation in the study.
- 21. Other concurrent medical conditions, therapy, or other condition that, in the Investigator's opinion, would interfere with the evaluation of the study medication, safety or efficacy, and/or put the subject at risk if he/she participates to the study.
- 22. Participation in an investigational device or drug study within 30 days prior to study treatment or plans to enroll in any other investigational study during participation in this study.
- 23. Study center personnel, close relatives of the study center personnel (e.g. parents, children, siblings, or spouse), employees or close relatives of employees at the Sponsor company.

	43QM1903 Clinical Study Protocol - QM1114 - LTS for LCL/GL	Dec id
♣ GALDERMA	To an action of the state of th	MA-40372

5.3 Medical History

Relevant history of surgical events and medical conditions shall be documented in the subject's study file and electronic case report form (eCRF) using medical terminology.

5.4 Previous and Concomitant Therapies

5.4.1 Definition

Previous therapies are defined as therapies that have been stopped within the 4 weeks preceding the screening visit or within timeframes specified in the inclusion/exclusion criteria.

Concomitant therapies are defined as follows:

- · any existing therapies ongoing at the time of the screening visit,
- any changes to existing therapies (such as changes in dose or formulation) during the course of the clinical study, or
- any new therapies received by the subject since the screening visit.

5.4.2 Categories

The following two categories are to be considered for previous and concomitant therapies:

- Drugs including but not limited to, prescription, over-the-counter (OTC), birth control
 pills/patches/hormonal devices, vitamins, herbal medicines/supplements, and homeopathic
 preparations.
- Medical and surgical procedures including, but not limited to, laser/radiation procedures, dermal fillers (area of treatment should be indicated), X-rays, surgeries, tooth extractions.

5.4.3 Recording

Previous and concomitant therapies are to be recorded in the subject's source documents and eCRFs

Concomitant therapies are to be reviewed at each visit and updated in the source documents and eCRFs as needed.

Any new concomitant therapy or modification of an existing therapy may be linked to an AE. A corresponding AE form should be completed to account for the change in therapy, except in some cases such as therapy used for prophylaxis, dose modification for a chronic condition, etc.

	Title	Doc id
• GALDERMA	43QM1903 Clinical Study Protocol - QM1114 - LTS for LCL/GL	MA-40372

5.4.4 Authorized Concomitant Therapies

Unless listed in prohibited concomitant therapies (see Section 5.4.5), all are authorized.

5.4.5 Prohibited Concomitant Therapies

The following therapies are prohibited because they may interfere with the efficacy and/or safety assessment of the study product.

- · Botulinum toxin of any serotype.
- Any other investigational new drug or device.
- · Any absorbable (temporary) or non-absorbable (permanent) material in the treatment areas.
- Facial aesthetic procedures (e.g., ablative skin resurfacing, laser treatment, micro needling, photodynamic therapy, tattooing or chemical peel) or any other procedures in the treatment area.
- · Facial surgery and eye surgery (including LASIK procedure).
- Medications that affect neuromuscular transmission such as curare-like depolarizing agents, lincosamides, polymyxins, anticholinesterases and aminoglycoside antibiotics.

If a prohibited therapy becomes a necessary treatment for best clinical interest of the subject or due to safety reason, the Medical Monitor (Section 11.9) should be notified, if time permits, to discuss possible alternatives prior to administration of a prohibited therapy.

If a subject receives a prohibited therapy during the clinical study, the Medical Monitor (Section 11.9) should be notified to discuss the subject's continuation in the clinical study.

5.5 Procedures/Reasons for Subject Discontinuation

An Investigator may decide to discontinue a subject from the clinical study for safety reasons.

Although the importance of completing the entire clinical study should be explained to the subject by the clinical study personnel, any subject is free to discontinue participation in this clinical study at any time and for whatever reason, specified or unspecified, and without any prejudice. No constraints are to be imposed on the subject, and when appropriate, a subject may be treated with other conventional therapy when clinically indicated.

When a subject does not complete the clinical study, he/she will be fully assessed, if such assessment is possible. The procedures designated for the Week 52/ET visit should be completed for all subjects discontinuing the clinical study and the appropriate eCRF should be completed.

All discontinuations and the reason for discontinuation are to be documented by the Investigator on the exit form. For discontinuation due to an AE, the AE form is to be completed. The Investigator should also ensure that the subject receives suitable therapy for the AE.

	43QM1903 Clinical Study Protocol - QM1114 - LTS for LCL/GL	Dec id
GALDERMA		MA-40372

Potential reasons for discontinuation are listed below:

Adverse Event: Complete an AE form.

 Withdrawal by Subject: Includes consent withdrawal, subject relocation, schedule conflicts, etc. Explain the reason for withdrawal in the comment section of the

eCRF exit form.

 Lost to Confirmed with two documented phone calls and a certified letter Follow-up: (delivery receipt requested) without answer. Explain in the comment

section of the eCRF exit form.

Other: This category is to be used for a subject who discontinues due to a

reason other than as specified in the predefined categories above. Explain the reason for discontinuation in the comment section of the

eCRF exit form.

A subject who has been enrolled cannot be replaced by another subject if he/she discontinues the clinical study for any reason. Additional subjects could be enrolled (randomized/assigned to treatment) in order to attain the number of evaluable subjects.

Pregnancies occurring during the screening period are considered screen failures; they should be recorded as such in the eCRF and no pregnancy form is to be completed. In case of a pregnancy occurring after the baseline visit, follow the procedures described in Section 7.2.5.2.3. The subject may remain in the study, but no invasive procedure should be conducted (e.g. no sample taken for lab test).

The Sponsor may also decide to prematurely terminate or suspend a subject's participation in the clinical study.

6. CLINICAL SUPPLIES

Details of the drug composition and excipients are provided in the current QM1114-DP Investigators Brochure. 12

6.1 Clinical Supply Identification and Use

6.1.1 QM1114-DP

The investigational product (QM1114-DP) will be supplied as a sterile solution for injection containing the drug substance, QM1114-DS. The drug substance is a BoNT Type A. QM1114-DS is diluted in a buffer solution.

At each treatment a total dose of 110 U of QM1114-DP will be administered as:

50 U (10 U per GL injection point)
 0.5 mL total (0.1 mL per GL injection point)

CONFIDENTIAL Page 36 of 86

AND

60 U (10 U per LCL injection point) 0.6 mL total (0.3 mL per treatment side/0.1 mL per LCL injection point)

6.1.2 Study Product Description

Table 2 Description and Usage of the Study Product

	Investigational product
Name of drug substance	QM1114-DS
Internal Code	QM1114-DP
Pharmaceutical Form	Solution for injection
Concentration	100 units/mL, buffered solution
CCI	
CCI	
001	
:CCI	
Dosage	At each treatment a total dose of 110 U of QM1114-DP will be administered as:
	50 units (10 U per GL injection point)
	0.5 mL total (0.1 mL per GL injection point)
	AND
	60 units (10 U per LCL injection point)
	0.6 mL total (0.3 mL per treatment site/ 0.1 mL per LCL injection point)
Route	Intramuscular injection
Dose regimen	Up to four (4) treatments
Location of treated area	Glabellar and lateral canthus areas

6.1.3 Subject Identification Number (SIN)

Each study participant who has signed the ICF will be entered into the eCRF system and a subject number will be assigned via the eCRF system. For the duration of the study, the subject will be identified using the subject number for all documentation and discussion.

Subject numbers will consist of the study center number followed by a consecutive number starting with 001 at each center. The subject numbers shall be allocated in ascending sequential

order within each center. If a subject is deemed not eligible for the study participation, the reason for screen failure should be specified. A screen failure cannot be re-screened.

A log/listing should be maintained by each site for all subjects who have signed the ICF. There should be sufficient information to link the eCRF to a study subject's source documents and medical records.

6.1.4 Method of Treatment Assignment

Not applicable. This is an open-label study.

6.1.5 Kit Number/Randomization Number

Not applicable. This is an open-label study.

6.1.6 Instructions for Use and Administration

QM1114-DP will be administered at baseline, and at follow up visits when the subject meets the re-treatment eligible criteria (see Section 6.1.6.3). Subjects may receive up to four (4) treatments during the study.

All treating Investigators will be trained in the administration technique prior to the study start. See also QM1114-DP Investigators Brochure. 12

Handling of accidently damaged or spilled study product is described in the Material Safety Data Sheet.

6.1.6.1 Treatment Procedure

6.1.6.1.1 Glabellar Lines

Prior to injection, the treatment area should be cleaned with a suitable antiseptic solution. An appropriately sized syringe and needle (e.g. 30-33 gauge needle) should be used to administer treatment.

Subjects will receive treatment with QM1114-DP in the GL at baseline, and at follow up visits when eligible (see Section 6.1.6.3). Each treatment includes 5 intramuscular (IM) injections of equal volume (0.1 mL) administered at 5 injection sites in the glabellar region (0.5 mL in total). The injections should commence in the procerus muscle followed by the corrugator supercilii muscles on each side, moving outwards from the median. All injections should be approximately 1 cm above the upper orbital rim and internal to the mid-pupillary lines (Figure 2).

In order to minimize risks of regional effect of the neurotoxin (e.g., eyelid ptosis), the investigator should use one thumb to apply pressure on the upper orbital rim while injecting. It is recommended that injection is not closer than 1 cm above the central eyebrow or the bony

2020-08-26 19:44

Effective date:

[figure not shown]
Doe id

MA-40372

🚣 GALDERMA

supraorbital ridge. Moreover, the tip and bevel of the needle should always be pointed away from the study subject.

Figure 2 Injection Sites for Treating Glabellar Lines

6.1.6.1.2 Lateral Canthus Areas

Prior to injection, the treatment area should be cleaned with a suitable antiseptic solution. An appropriately sized syringe and needle (e.g. 30-33 gauge needle) should be used to administer treatment.

Subjects will receive treatment with QM1114-DP in the LCL at baseline, and at follow up visits when eligible (see Section 6.1.6.3). At each treatment visit, a total dose volume of 0.6 mL divided into six equal aliquots (0.1 mL per injection site) will be administered intramuscularly in the lateral canthus areas, 0.3 mL per side.

There are two options for the injection sites in the lateral canthus areas; see Figure 3 and Figure 4 below. The injection site option for each subject is based on Investigator discretion, and should be consistent for the right and left treatment sides.

Injections should be performed at a 20-30° angle to the skin, with bevel of needle tip pointed up and away from the eye and very superficial. All injection points, three per side, should be at the external part of the orbicularis oculi muscle and sufficiently far from the orbital rim (at least 1 - 2 cm). The injection points should be separated by 1-1.5 cm distance.

[figure not shown]
When lines in the lateral canthal region appears both above and below the lateral canthus, inject per Figure 3. In case lines in the lateral canthal region are mainly below the lateral cantus, inject per Figure 4.

The anatomical landmarks can be more readily identified if observed and palpated at maximum smile. Care must be taken to avoid injecting the zygomaticus major/minor muscles to avoid lateral mouth drop and asymmetrical smile.

Figure 3 Injection Sites for Treating LCL Option 1

Figure 4 Injection Sites for Treating LCL Option 2

6.1.6.2 Post-treatment Care

Following treatment administration, subjects will be monitored at the study center for 30 minutes.

Subjects will be instructed to avoid applying pressure, rubbing or massaging the treated areas, or lying face down for 4 hours after treatment.

6.1.6.3 Treatment Regimen

Subjects will receive up to four treatments with QM1114-DP in their glabellar and lateral canthal lines during the study period, each treatment cycle is at least 12 weeks apart. Follow-up assessments for treated subjects are conducted at Day 7 and Day 14 post-treatment. All subjects are followed up every 4th week for a period of up to 52 weeks.

The following conditions are required to be met for re-treatment post-baseline:

- · It has been at least 12 weeks since the previous treatment in the intended area
- For GL re-treatment:
 - Moderate (grade 2) or severe (grade 3) rhytides at maximum frown as assessed by the Investigator (ILA).

CCI

- For LCL re-treatment:
 - Moderate (grade 2) or severe (grade 3) rhytides at maximum smile as assessed by the Investigator (ILA).

CC

- In order to treat LCL, both sides should meet severity criteria and be treated at the same visit.
- There are no ongoing adverse events assessed as related to the treatment, which could
 preclude the subject from re-treatment.
- Subject agrees to receive re-treatment.
- If subject is a female of child-bearing potential, agrees to take a pregnancy test and test result
 must be negative in order to receive re-treatment.
- There is no other medical or surgical condition that would put the subject at undue risk in case he/she receives an additional treatment cycle, according to investigator's judgment.

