Appendix 5 Focused Physical Examination Form Example83
Appendix 6 Adverse Events Potentially Suggestive of Remote Spread of Toxin85
SIGNED AGREEMENT OF THE CLINICAL STUDY PROTOCOL86

List of Tables

Table 1	Schedule of Assessments	16
Table 2	Description and Usage of the Study Product	37
	List of Figures	
Figure 1	Study Flow Chart	15
Figure 2	Injection Sites for Treating Glabellar Lines	39
Figure 3	Injection Sites for Treating LCL Option 1	40
Figure 4	Injection Sites for Treating LCL Option 2	40

SYNOPSIS				
Clinical Study Title: A Multicenter, Open-Label Study to Evaluate the Safety of QM1114-DP for the Long-term				
	Treatment of Moderate to Severe Glabellar Lines and Lateral Canthal Lines (READY - 4) Short Title: QM1114-DP Long-term Treatment of GL and LCL			
	satirent of GL and LGL			
Clinical Study Population:	Male and female subjects, 18 years of age and older, with moderate to severe glabellar lines (GL) at maximum frown and moderate to severe bilateral lateral canthal lines (LCL) at maximum smile.			
Clinical Study Design:	This is a phase 3, multicenter, open-label study to evaluate the safety of QM1114-DP for the long-term treatment of moderate to severe GL and LCL.			
	Eligible subjects will receive up to 4 treatments of QM1114-DP in the GL and/or LCL and will be monitored for safety and efficacy over a period of up to 52 weeks.			
	The first treatment will be administered at Day 0 (Baseline). Re-treatments can be administered at any of the follow-up visits from Week 12 to Week 40, provided that the subject is eligible for re-treatment and there has been at least 12 weeks since the last treatment. Follow-up visits for treated subjects are conducted at Day 7 and Day 14 after each treatment. Follow-up visits, i.e. not treatment dependent, are scheduled at Week 4, 8, 12, 16, 20, 24, 28, 32, 36, 40, 44, 48 and 52.			
	To ensure a sufficient amount of long-term safety data is included in the database per ICH E1 guidelines, approximately 900 subjects will be enrolled; all subjects will be followed for at least 24 weeks and at least 300 subjects will be followed up to 52 weeks. The study may be stopped when at least 300 subjects have completed the Week 52 study visit.			
Target Indication:	This study is designed to evaluate the safety of QM1114-DP for the long- term treatment of moderate to severe GL and LCL.			
Total Number of Subjects (Planned):	Approximately 900 subjects will be enrolled.			

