6.3.5 Dose Modification

Dose modifications are not permitted.

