 - If the subject is a female of childbearing potential, collect urine for UPT and complete
 pregnancy test (see laboratory manual for additional procedures). Document the result.
 A negative result is required for re-treatment.
 - Collect blood sample for neutralizing antibody testing prior to re-treatment (Section 7.2.4).
 - The Investigator or designee should prepare the treatment accordingly and complete the required documentation and eCRF (Section 6.1.6).

- Prior to injection, clean the subject's treatment areas with a suitable antiseptic solution.
- The Investigator will administer the treatment(s). See Section 6.1.6.1 for treatment procedure requirements. Following treatment administration, subjects will be monitored at the study center for 30 minutes. (Section 6.1.6.2)
- Obtain the subject's post-treatment vital signs (blood pressure, heart rate, and respiratory rate). Vital signs are to be taken seated after 10 minutes rest (Section 7.2.2).
- Ask the subject about AEs using an open-ended question. Record all events, as appropriate, on the corresponding eCRF form(s).
- · Record post-treatment concomitant therapies/procedures.
- Schedule the next visit (Day 7 ±1 day). NOTE: Treatments must be at least 12 weeks apart.

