9.1.4 Data Presentation and Graphics

All statistical analyses will be descriptive, and performed using the SAS® system (version 9).

In general, continuous data will be summarized using n (number of observations), mean, standard deviation, median, minimum and maximum value, while categorical data will be presented by frequency and percentage. Graphs may be used as appropriate.

Subject disposition, demographics and baseline characteristics, medical history, concomitant medication and procedures, and number of treatment cycles will be summarized.

All analyses of AEs will be done both for the whole study and per cycle. Treatment-emergent Adverse Events (TEAEs) will be tabulated in frequency tables by System Organ Class (SOC) and Preferred Term (PT) based on MedDRA. Additional summary tables will be provided for AEs that are considered serious (SAEs), related to the study product(s), and AEs leading to discontinuation. For related AEs, action taken, intensity, duration, and onset will be presented. For a given AE, a subject will be counted once even if he/she has experienced multiple episodes of that particular AE.

Consistency of the AE incidences will be analyzed in subgroups by gender, prior use of botulinum toxin, race, Fitzpatrick skin type, treatment area, and center.

In addition, AEs with an onset prior to the baseline visit will be listed separately.

	Title 420M1003 Clinical Study Protocol - OM1114 - LTS for LCL/CL	Doc id
♣ GALDERMA	43QM1903 Clinical Study Protocol - QM1114 - LTS for LCL/GL	MA-40372

Results from physical examination, vital signs, clinical chemistry and hematology tests, and presence or absence of NAB will be summarized by visit and cycle. For continuous data both the value at each visit as well as the change from baseline will be used.

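### The re-treatment rules contradict each other on the 12-week interval (any treatment or the same area) and on whether one area may be dosed alone, which also makes the per-cycle summaries ambiguous

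*Protocol*

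**What the plan says.** **Interval.** The Section 3 criteria require: "It has been at least 12 weeks since the previous treatment". The synopsis says the same ("there has been at least 12 weeks since the last treatment"). Sections 8.1.3 and 8.1.4 carry the reminder "NOTE: Treatments must be at least 12 weeks apart". None of these limits the interval to an area. Section 6.1.6.3 opens in the same sense ("each treatment cycle is at least 12 weeks apart"), but its first re-treatment condition is "It has been at least 12 weeks since the previous treatment in the intended area", followed by separate severity criteria for GL and for LCL.

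**Dose.** Section 6.1.1, Table 2 and the synopsis fix the dose: "At each treatment a total dose of 110 U of QM1114-DP will be administered as" 50 U in the GL and 60 U in the LCL, joined by a capitalised AND. Section 6.3.5 adds: "Dose modifications are not permitted". The synopsis design text and Section 3, however, allow treatment of GL, LCL or both, and Section 6.1.6.3 lets each area qualify on its own severity grade.

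**Limit.** Subjects may have up to four treatments (Sections 3, 6.1.6 and 6.1.6.3). No passage says explicitly whether a treatment is a session or an injection series in one area.

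**Use of cycle.** Section 9.1.4 states: "All analyses of AEs will be done both for the whole study and per cycle". Examination, vital-sign, laboratory and neutralizing antibody (NAB) results are summarised by visit and cycle. The secondary endpoints in Section 2.1.2 are response rates at each visit within each cycle.

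**The concern.** An investigator at a Week 12 to 40 visit needs one answer to two questions: may this area be injected today, and what is given if only one area qualifies? The protocol gives two answers to each. Section 8.1.4 contains both interval rules: it refers to Section 6.1.6.3 for the criteria and then repeats the unrestricted 12-week note. A statistical analysis plan cannot repair this, because it does not tell a site when or what to inject.

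The primary objective is the safety of repeated injections. With up to 36 centers, two sites could each follow the text and still produce different treatment spacing, and the same schedule could be recorded as a deviation at one site and not at another. If the two areas drift onto different visits, an adverse event (AE), NAB result or severity score can belong to cycle 2 for one area and cycle 1 for the other.

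**Working it through.** **Inputs**
- GL: 5 points at 10 U; LCL: 6 points at 10 U (Sections 6.1.1, 6.1.6.1.1, 6.1.6.1.2).
- Both areas are treated on Day 0. Re-treatment visits are Weeks 12, 16, 20, 24, 28, 32, 36 and 40 (Section 3).
- Interval: 12 weeks from any treatment, or 12 weeks from the last treatment in the same area.
- Nominal weeks are used and visit windows ignored.

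**1. Stated dose.** 5 × 10 + 6 × 10 = 50 + 60 = 110 U. The plan's figure reproduces.

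**2. The conflict on one subject.** GL alone is re-treated at Week 12; LCL was last treated on Day 0.
- Same-area clock at Week 16: 16 − 0 = 16 weeks, at least 12, so LCL may be injected.
- Any-treatment clock at Week 16: 16 − 12 = 4 weeks, so it may not. The first permitted visit is 12 + 12 = Week 24.

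The minimum gap between treatment days is thus 4 weeks under one rule and 12 under the other.

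**3. Number of treatment days.** Within one area, 12-week spacing on Weeks 12 to 40 allows at most three re-treatments. The four possible patterns are (12, 24, 36), (12, 24, 40), (12, 28, 40) and (16, 28, 40). With Day 0 this makes four per area.
- Any-treatment clock: at most 4 treatment days.
- Same-area clock, limit of four read as sessions: at most 4 treatment days, but the gap can still be 4 weeks.
- Same-area clock, limit of four read as per area (an assumption): GL at 0, 12, 24, 36 and LCL at 0, 16, 28, 40 gives 0, 12, 16, 24, 28, 36, 40, that is 4 + 4 − 1 = 7 treatment days.

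**4. How often the rules diverge.** One area has 1 + 8 + 15 + 4 = 28 permitted schedules (0, 1, 2 or 3 re-treatments), so two areas have 28 × 28 = 784 pairs under the same-area clock with the limit read per area. Enumeration finds 516 of these (516/784 = 66%) with two treatment days less than 12 weeks apart, which the any-treatment rule forbids. This is a share of permitted schedules, not a forecast of subjects.

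**5. Dose.**
- Ceiling in total: 4 × 110 = 440 U by session, or 4 × 50 + 4 × 60 = 440 U by area.
- In any window shorter than 12 weeks, each area can be injected once: 50 + 60 = 110 U under either clock.
- A single-area session gives 50/110 = 45% or 60/110 = 55% of the dose stated for each treatment. With single-area sessions allowed, four sessions total from 110 + 3 × 50 = 260 U to 440 U; with 110 U fixed they total exactly 440 U.

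**6. Per-cycle summaries.** In the step 2 example with LCL injected at Week 16, a Week 14 AE falls in GL cycle 2 and LCL cycle 1. NAB samples are due before each re-treatment and 4 weeks after each (Section 7.2.4), so the Week 16 sample is both the one 4 weeks after the GL session and the one before the LCL session.

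**The case against.** Five points deserve weight.

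- **One reading satisfies every interval passage.** A schedule that keeps 12 weeks between all treatments also meets the same-area condition. That is true, but the same-area condition is the operative eligibility list, and it permits an injection that Section 3 forbids. A site following it is not misreading the protocol.
- **The dose conflict may be loose wording.** Section 1.2.2 names 50 U, 60 U and 110 U as doses to be evaluated. Sections 6.1.6.1.1 and 6.1.6.1.2 fix each area's volume and give it when that area is eligible. The dose per area never varies, so a single-area session need not be a dose modification. This stands as far as it goes, but the text fixing 110 U at each treatment still does not fit it.
- **The limit of four is worded per subject.** Reading it as four sessions is natural. A reader might infer that the protocol permits 7 treatment days; that needs a per-area limit which the protocol does not state.
- **Cycle derivation may sit in the statistical analysis plan.** Section 9.1 leaves data conventions to it, and it is not shown. A reader might infer that one subject-level cycle is planned and that LCL scores after a GL-only session will be counted as LCL response. The text does not say so, and Section 2.1.2 lists GL and LCL endpoints separately.
- **The treatment-area AE subgroup is not in itself an error.** Every subject receives both areas on Day 0, but the areas can differ at re-treatment. The subgroup mainly confirms that single-area sessions are expected.

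**Conclusion.** The contradiction is real and lies in operative text. The interval is 12 weeks from any treatment in the synopsis, Section 3, Sections 8.1.3 and 8.1.4 and the opening of Section 6.1.6.3, but 12 weeks in the intended area in the Section 6.1.6.3 condition. The consequence is a minimum gap of 12 or 4 weeks. The dose at a single-area session and the unit counted by the limit of four are also unsettled; 7 rather than 4 treatment days follows only if that limit is per area.

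Two broader inferences are not supported. Permitted exposure is not undefined, since the ceiling of 440 U, and of 110 U in any window shorter than 12 weeks, holds on every reading. Nor does every analysis depend on the cycle: whole-study AE summaries, disposition and demographics do not. What is ambiguous, if the areas are treated at different visits, is the allocation of AEs, NAB results and severity scores in the per-cycle summaries. The figures rest on nominal visit weeks.

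**What to change.** Reconcile the synopsis, Section 3, Section 6.1.1, Table 2, Section 6.1.6.3 and Sections 8.1.3 and 8.1.4 in one amendment, so that three things agree throughout:

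1. whether the 12-week interval runs from any treatment or from treatment in the same area;
2. whether the limit of four counts sessions or treatments per area;
3. how the dose is worded for a session in which only one area is treated, including how this relates to Section 6.3.5.

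This review takes no view on which clinical rule is right.

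If staggered treatment of the two areas remains permitted, count GL and LCL efficacy cycles separately, each from an injection in that area. Tabulate per-cycle AEs by injection session and by the area or areas injected at that session. Whole-study tables stay as they are.

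The cost is amendment wording and a short definition in the statistical analysis plan. Section 6.3.4 already has injection details recorded in the eCRF, so the area-level counts should need no new data collection.
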